4.1 Description

Hyperbaric oxygen given immediately preceding intracranial stereotactic radiosurgery

4.2 Treatment Regimen

Prior to the day of treatment, each patient will receive an orientation to the hyperbaric chambers located in the hyperbaric medicine department within radiation oncology. A “test drive” will be performed with the patient in the chamber with air rather than 100% oxygen. This will verify the patient’s ability to equalize pressure in the middle ear and will assure that he or she is not claustrophobic. A small percentage of patients (estimated at 15%, based on prior experience) may be unable to achieve pressure equalization in the middle ear. These patients will be offered placement of a tympanostomy tube to facilitate HBO treatment and to enable continuation with the protocol, a simple procedure performed typically by a Physician’s Assistant in DHMC’s Section of Otolaryngology.

On the day of SRS, during HBO treatment the patient will receive oxygen under pressure while lying supine inside the hyperbaric chamber. HBO will be given at 2.4 ATA. Compression will occur at 3.77 feet/minute. The patient will stay at depth for 30 minutes. Decompression will be performed over a 5-minute time span.

Patients then will be transported from the HBO chamber via stretcher to the SRS treatment area while receiving 100% oxygen via non-rebreather face mask @15L/minute to help maintain oxygen saturation.

Patients then will receive radiosurgery for their metastases as detailed below (Section 5.3 – “SRS Treatment Visit”).

A stopwatch will be used to document the time elapsed from when the patient exits the hyperbaric chamber to when he/she starts receiving SRS (“beam-on”). The goal of this time interval should be kept at ≤ 15 minutes. Elapsed time from leaving the hyperbaric chamber to completion of SRS will be recorded as well.

4.3 Acute HBO toxicity

We do not anticipate patients experiencing toxicities in conjunction with their HBO treatments. All will have undergone pre-screening for claustrophobia and barotrauma.

The likelihood of a seizure in conjunction with HBO treatment is less than one in a thousand (in the general population).

In the very unlikely event of a tonic-clonic seizure, the chamber will be brought to surface after air breaks and after tonic-clonic movements have subsided and regular respirations have resumed. Then the patient will be removed from the chamber and transported to the DHMC Emergency Department for further evaluation and management.

4.4 Prior and Concomitant Therapy

Patients will continue on the medications prescribed by their treating providers.

Patients who are taking anticonvulsants upon enrollment in the study will continue those medications as prescribed. Palliative and supportive care for disease-related symptoms will be offered to all subjects enrolling on this trial (which is our standard of care), and these will be continued as appropriate during the phases of this protocol. Details about interventions and concomitant medications will be collected.

Treatment with disulfiram is not allowed in this study since disulfiram inhibits superoxide dismutase. Patients should not receive cis-platinum chemotherapy just prior to their hyperbaric oxygen treatments.

5 Study Procedures (see attached table, Section 14.1)

5.1 Visit 1 – “Initial consultation visit”

At this “visit” the radiation oncologist screens potential patients, discusses risk/benefits of the study with eligible patients, and provides patients with information about the study. Patients will also have a consultation with neurosurgery. During this time the study consent will be completed (along with any further required screening procedures, including blood work). Although we are considering the consultations with radiation oncology and neurosurgery to be part of the same “visit,” for logistical reasons the consultations with the radiation oncologist and neurosurgeon may take place on different days. Chest imaging is required (in preparation for HBO to exclude pulmonary contraindications) if the patient has not had a chest imaging in the prior year. We estimate 25% of patients will require a chest imaging, though it seems likely that in this heavily treated cancer population the number will in actuality be lower than this estimate.

Information collected at Visit 1
Inclusion /Exclusion criteria
History and Physical Examination
EORTC Quality of Life C-30 and BN20

Karnofsky/Zubrod Performance Status
St. Louis University Mental Status Exam
Complete Blood Count (within 30 days of SRS treatment)
Comprehensive Metabolic Profile (within 30 days of SRS treatment)
*Blood sample for biomarkers (pre-TX)
Review of prior MRI of the brain
Pathology confirmation
Pregnancy Test, if applicable (within 14 days of SRS treatment)
Chest imaging, if indicated

*If the patient is enrolled in the biomarker sub-study, a blood draw will be performed prior to the HBO and SRS treatments to test NSE and S100 β levels.

5.2 Visit 2 – “Pretreatment visit”

At this “visit” the patient will have a consult for HBO treatment, and then will have a practice dive with air in the hyperbaric chamber. The patient will also have a radiotherapy-planning MRI, a fitting for the [VisionRT open face mask system](#), and a CT-based simulation of the SRS treatment for radiation therapy treatment planning. Although these items are all considered part of the “pre-treatment visit,” for logistical reasons some of the items may be scheduled on different days.

Information collected at Visit 2
HBO consult with “dry run”
RT-planning brain MRI
CT-based RT simulation (including fitting of - VisionRT open face mask)

5.3 Visit 3 – “SRS Treatment Visit”

At this visit the patients will undergo HBO treatment (as detailed in Section 4.2 above), followed by radiation therapy (SRS).

5.3.1 Principles:

Stereotactic radiosurgery (SRS) requires precise target definition using volumetric (3D conformal) techniques. Treatment delivery is accomplished with millimeter-precision through the combination of precise pre-treatment MRI imaging, accurate image co-registration of planning MRI scans and CT-simulation datasets, and precise frame-based treatment with image-guidance on the linear accelerator at time of treatment delivery.

5.3.2 Equipment:

Accelerator x-ray beams (photons) with nominal energy of at least 4 MV and not greater than 20 MV. The accelerator must have available cone-beam CT (CBCT) imaging capabilities to assure accurate set-up at the time of treatment delivery.

5.3.3 Protocol Volume Target Definitions:

All treatment planning will be based upon the following target definitions. Treatment will be prescribed to the PTV, which will be derived from the GTV, as follows:

5.3.4 Gross Tumor Volume (GTV):

This is the volume occupied by radiographically visible disease as per postoperative and pre-irradiation MRI. The T1-MR image with contrast is usually the optimal imaging study. Appropriate fusion of the MRI with the planning CT scan is required for accurate treatment delivery.

5.3.5 Planning Target Volume (PTV):

The PTV accounts for uncertainties in imaging, registration, and patient set-up, and also incorporates the potential for microscopic disease extension. For unresected metastases treated in the VisionRT open face mask, the additional margin from GTV to PTV will be 2 mm in all dimensions. For resected metastases treated in the VisionRT open face mask, the additional margin will be 3 mm in all dimensions.

5.3.6 Timing of Radiotherapy:

Radiation therapy will be delivered following the patient's exit from the HBO chamber. Every effort will be made to begin radiation treatment within 15 minutes of the patient's exit from the chamber. The time between exit from the chamber and beam-on will be recorded as part of the patient's treatment record.

5.3.7 Target Dose:

In general, the target dose to the margin of the PTV will be prescribed as per RTOG 90-05, which is considered the current standard of care [28]. However, the target dose may be modified to respect normal tissue tolerances (see below), as per clinical judgment of the prescribing radiation oncologist and the consulting neurosurgeon:

Target diameter	Dose to target margin
Up to 2.0 cm	20 Gy
2.1 – 3.0 cm	18 Gy
3.1 – 4.0 cm	15 Gy
4.1 – 5.0 cm	12 Gy

5.3.8 Normal Tissue Tolerance:

Dose prescriptions will take into account the tolerances of surrounding normal tissues, such as brainstem, optic nerves, optic chiasm, and motor cortex. Target dose to the margin of the PTV may be modified to avoid excess dose to such sensitive tissues, per the clinical judgments of the prescribing radiation oncologist and the consulting neurosurgeon.

5.3.9 Optional Blood Draw for Markers

If the patient is enrolled in the blood marker sub-study, a blood draw will be performed the day following the SRS treatment.

5.4 Follow-up visits

At each of these visits, the patient will undergo a follow-up MRI scan (with sequences including dynamic susceptibility contrast (DSC) perfusion, apparent diffusion coefficient (“ADC”), and single voxel proton MR spectroscopy if radionecrosis and/or local tumor recurrence is suspected on the standard MRI sequences) as well as history and physical exam with the radiation oncologist. Bloodwork will be drawn at the first follow-up visit (including CBC, CMP, and biomarkers (for participating patients only).

These visits will occur at the following intervals:

Optional follow-up visit for blood marker study – Day after SRS

First follow-up visit (“Visit 4”) – 4-6 weeks after SRS;

Visits 5 through 12 – at 3-month intervals after the initial follow-up till the conclusion of the study (two years following SRS).

Further follow-ups (off-protocol) will continue as per standard of care:

Visits 13 through 15 – at 4-month intervals after Visit 12;

Visits 15 through 18 – at 6-month intervals after Visit 15;

Visits 19+ – annual follow-up visits after Visit 18.

Information collected at each follow-up visit
History and Physical Examination
EORTC QLQ C-30 and BN-20
St. Louis University Mental Status Exam
MRI of the brain
(Plus bloodwork drawn at Visit 4 including CBC, CMP, and biomarkers)

6 Statistical Plan

6.1 Statistical Methods

For the primary outcome variable of feasibility, the twenty evaluable patients will be analyzed on the basis of the amount of time required from leaving the HBO chamber to beginning SRS for the target lesion (T1).

The goal for each patient (as discussed in Section 2.2) is for T1 to be no greater than 15 minutes. In a Phase I trial of HBO treatment in coordination with fully fractionated head-neck cancer XRT, DHMC established a track-record of an average of only eight minutes from time of leaving the HBO chamber to “beam on” for this patient group [22]. However, set-up for SRS treatment is more complex, involving placement of a head-frame and performance of a CT-scan prior to SRS treatment. These may extend the time interval required for patient set-up after leaving the HBO chamber.

We anticipate a learning curve for the team members of this study. Therefore, stopping rules are as outlined in Section 7.4: no more than 20% of first ten patients treated within

30 minutes of HBO; and no more than 33% of first fifteen patients treated within 30 minutes of HBO.

The primary endpoint of feasibility is defined as having been achieved if more than 50% of the 20 evaluable patients start SRS treatment within 30 minutes of leaving the HBO tank: in other words, T1 is ≤ 30 minutes for $>50\%$ of evaluable patients.

For the secondary endpoints, using Cox proportional hazards models, and Kaplan-Meier survival statistics, the overall group of 20 will be analyzed for event-free survival and compared against a matched set of patients from our institution (see below for methodology). This match will be based on tumor size, resection status, and histology-specific graded prognostic assessment (GPA). The GPA is a validated, widely accepted prognostic scale predictive of survival for patients presenting with brain metastases. Diagnosis-specific GPA calculation is based on published criteria including tumor histology, presence of systemic metastases, number of brain metastases, age, performance status, and breast-cancer specific molecular markers [29-31]. Further demographic and treatment data will also be collected, including: gender, subtotal resection versus gross total resection (if tumor resected), tumor diameter (prior to first treatment, whether surgery or SRS), SRS target volume (PTV), and prescribed dose to the PTV. The secondary outcome variables will be the first occurrence of the event of interest and also the time until the first occurrence of the event of interest. These events include: intracranial recurrence at SRS site, intracranial recurrence at a distant site, whole brain XRT, second SRS (classified as either local or distant), third SRS (classified as local or distant), radionecrosis at the SRS site, and death.

A retrospective database pertaining to Dartmouth-Hitchcock's experience with stereotactic radiosurgery in the treatment of brain metastases is being collected through Study 00030625 (PI [name]). Pertinent matching variables, along with demographic variables, treatment variables, and outcome variables for the control population are available on 00030625. The matching variables (histology, lesion size, resection status, and calculated GPA) will be used to identify a control population in the Study 00030625 that match 1:1 against the D12129 enrolled patient population.

Specifically, patients with similar tumor histologies will be matched against histologies found in the D12129 patient population, falling into one of six categories: (1) non-small cell lung cancer, (2) melanoma, (3) breast cancer, (4) renal cell cancer, (5) GI cancers, and (5) other histologies. Once a histologic match is identified, the patient is then matched by resection status (either unresected or resected). The third matching variable is then GPA. If an exact GPA match is not available in the 000030625 data base, then a patient with a higher GPA will be selected, with the control patient's GPA as near as possible to that of the corresponding D12129 patient (thereby, if anything, biasing the survival outcome data slightly against the D12129 data set). Lastly, the fourth matching variable is tumor size (i.e. maximum tumor diameter) at time of treatment (a categorical variable, either below or above 2.0 cm). If an exact match for the fourth variable is not available in the 000030625 data base, then size will be matched as closely as possible to the 2.0 cm cut-off from those patients available in this historical database. These

matching patients identified in 000030625 data base will serve as the control group for the D12129 study.

Once the control group patients have been selected, their data will be extracted from the 000030625 database in de-identified form. These data will be reviewed by an “honest broker” to assure proper de-identification and HIPAA compliance. These de-identified control group data will then be merged with the D12129 dataset. Analysis of this combined data base then will allow comparison of HBO-treated and control patients in terms of event-specific outcome parameters, with events including: death, local intracranial recurrence, distant intracranial recurrence, whole brain radiation therapy, and repeat SRS (either local or distant).

Exploratory variables will include QOL data and tumor markers. Comparisons for change in markers before versus after HBO-SRS treatment will be performed for the entire group of twenty patients. Also comparisons will be performed for subgroups (including comparisons of those with resections versus those without, and of those above 2.0 cm diameter versus those below).

Time line for completion of the study is 5 years. We anticipate accrual of the 20 patients in the first three years (0-36 months). Follow-up is anticipated to be a minimum of one to two years for each surviving patient (13-48 months). Manuscript preparations and submissions should occur in the fourth and fifth years (48-60 months).

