2.2 Primary Study Endpoints

Demonstrate that coordination of HBO with SRS treatments is feasible.

For HBO sensitization of SRS patients to be feasible, patients must receive radiation treatment within a time frame in which pO₂ levels are meaningfully elevated. Since intratumoral oxygen levels within the brain remain elevated for about 30 minutes after exposure to hyperbaric oxygen [17], feasibility of HBO-SRS treatment requires that a patient at least begin SRS within 30 minutes of leaving the HBO chamber. Evaluation of the ability to achieve this goal will be the primary study endpoint. We will measure time from end of “dive” to start of SRS treatment. Goal will be to achieve “beam on” within 15 minutes of leaving the chamber. Total time for treatment to one isocenter (from first arc’s beam-on to last arc’s beam-off) using SRS in this study is estimated at 10 minutes (three SRS arcs, each 2 minutes, plus set-up time between the first and second and between the second and third arcs, each 2 minutes, totaling 10 minutes). We anticipate a learning-curve as HBO and therapy staff to develop skill sets for optimizing time across the various steps of the procedure:

- Leaving the HBO chamber
- Fitting the - [VisionRT open face mask system](#)
- Positioning the patient on the table
- Imaging the patient to confirm position
- Reviewing/approving images for treatment

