14.3 HBO Treatment Protocol (including “dry run”)

HBO Protocol

14.3.1

Prior to the first visit, any contraindications to hyperbaric treatment will be reviewed. Patients will be scheduled for a chest X-ray, if indicated.

14.3.2

During the first visit patients will have a hyperbaric focused history and physical, and the results of any imaging tests will be reviewed.

Patients will then have a familiarization dive in the chamber. Prior to entering the chamber the patients will have an otoscopic exam. Patients will be placed in the chamber, and the chamber will be pressurized with air to 2.4 ATA. The pressure will then be released. After the patients come out of the chamber they will then have another otoscopic exam.

Patients who have difficulty with equalizing the pressure within their ears will be offered pressure-equalization tubes.

14.3.3

On the treatment day, patients will come first to radiation oncology, where the procedure for the day will be reviewed. The patient will then return to hyperbarics to begin the hyperbaric treatment.

The patients will remove jewelry, watches and any other items that are not approved for use in the chamber (e.g. electronics, matches, lighters, metal objects, cigarettes, car keys, coins/money, batteries, watches, shoes, hand warmers, newspapers, books, magazines, loose medications, stockings, hearing aids). They will remove their street clothes and put on 100% cotton gowns provided by the hyperbaric center.

The chamber will be pressurized to 2.4 ATA at a compression rate (breathing oxygen) of approximately 1 – 3 psi per minute, depending on patient tolerance. The patient will receive hyperbaric oxygen for 30 minutes starting at the time the chamber reaches 2.4 ATA. The decompression rate will be approximately 2-3 psig/fsw per minute depending on patient tolerance. When the treatment is finished, the patient will be removed from the

chamber and transported to the radiation oncology suite via stretcher while receiving 100% non-rebreather face mask @ 15L/min to help maintain oxygen saturation.

The patient will have the Gill-Thomas-Cosman head frame or the VisionRT open face mask placed. Pre-treatment imaging studies then will be performed on the radiation therapy treatment unit, to assure accurate localization of the planned treatment. Stereotactic radiosurgery treatment may then proceed.

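### The feasibility endpoint scores only the time from chamber exit to beam-on, so an undelivered HBO session counts against feasibility only if SRS also starts late

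*Combined protocol and SAP*

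**What the plan says.** The primary objective (2.1.1) is to show that HBO and SRS can be coordinated. Section 2.2 gives the reason for the endpoint: "patients must receive radiation treatment within a time frame in which pO₂ levels are meaningfully elevated". It turns this into a timing condition: "feasibility of HBO-SRS treatment requires that a patient at least begin SRS within 30 minutes of leaving the HBO chamber".

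Section 6.1 takes as its variable "the amount of time required from leaving the HBO chamber to beginning SRS for the target lesion (T1"). Feasibility is achieved if "more than 50% of the 20 evaluable patients start SRS treatment within 30 minutes of leaving the HBO tank". Section 7.4 stops the study for infeasibility if no more than 2 of the first 10, or 5 of the first 15, patients are treated within 30 minutes of chamber exit.

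The exposure is specified only as a procedure. Section 4.2: "The patient will stay at depth for 30 minutes". Attachment 14.3: "The patient will receive hyperbaric oxygen for 30 minutes starting at the time the chamber reaches 2.4 ATA". The timing instruction in 4.2 is "A stopwatch will be used to document the time elapsed from when the patient exits the hyperbaric chamber to when he/she starts receiving SRS", plus the time from exit to the end of SRS.

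The only text that bears on who is evaluable is 3.4.3: patients withdrawn under 3.4.1 within one year of enrollment do not count toward the twenty and are replaced. The reasons in 3.4.1 include subject request, unacceptable adverse events during HBO or SRS, and physician judgment. A shortened dive is not named.

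**The concern.** The rationale in 2.2 presupposes the exposure: tumor oxygen can still be raised 30 minutes after exit only if the session raised it. The scoring rule drops that premise. Consider a patient brought out early for ear pain or anxiety who remains on study and reaches beam-on 12 minutes later. T1 is 12 minutes and the patient counts as a success. If the same patient is withdrawn, a substitute takes the place. Either way, failure to deliver HBO does not count against feasibility unless SRS also fails to start within 30 minutes of exit.

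At stake is the meaning of the only primary endpoint. A positive result could rest partly on patients who did not receive the planned intervention, or on a denominator from which those who could not tolerate it were removed. If achieved exposure is not recorded, a reader could not tell.

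**Working it through.** The plan gives no null rate, significance level or power for the feasibility endpoint, so there is no calculated figure to reproduce. Its rule arithmetic is correct: 2/10 = 20%, 5/15 = 33%, and more than 50% of 20 means at least 11.

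**Step 1: how each kind of patient is scored in the primary analysis**

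| Treatment-day course | Score under 6.1 and 3.4.3 |
|---|---|
| Full session, T1 ≤ 30 min | Success |
| Full session, T1 > 30 min | Failure |
| Shortened session, not withdrawn, T1 ≤ 30 min | Success |
| Shortened session, not withdrawn, T1 > 30 min | Failure |
| Shortened session, withdrawn under 3.4.1 within a year | Replaced |

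The third and fifth rows are the gap. A seizure in the chamber does not fall in the third row: 4.3 sends that patient to the Emergency Department, and 3.4.1 lists the event as a reason for discontinuation.

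**Step 2: at the boundary (no assumed rates)**

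Eleven timely starts, one of them after an incomplete dive, give 11/20 = 55% (met) as written. Requiring delivery as well gives 10/20 = 50% (not met).

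**Step 3: size under assumed rates**

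Let t = P(T1 ≤ 30 min) and e = P(session delivered as planned). The documents state neither, so both are assumptions, taken as independent.

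- Current rule: P(X ≥ 11), X ~ Bin(20, t).
- Joint rule, with aborted sessions kept in the denominator: P(X ≥ 11), X ~ Bin(20, t × e).

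For example, t = 0.60 and e = 0.90 give t × e = 0.54 and P(X ≥ 11) = 0.556.

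| t | Current rule | Joint, 5% incomplete | Joint, 10% incomplete | Joint, 15% incomplete |
|---|---|---|---|---|
| 0.60 | 0.755 | 0.661 | 0.556 | 0.447 |
| 0.70 | 0.952 | 0.905 | 0.835 | 0.740 |
| 0.80 | 0.997 | 0.990 | 0.970 | 0.928 |

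With only 1% or 2% incomplete at t = 0.60, the joint figures are about 0.74 and 0.72. Under independence, the current-rule column is the same whether incomplete-dive patients stay or are replaced, because a substitute meets the time limit with the same probability t. What changes is the distortion: patients who stay can inflate the success count, and patients who are replaced disappear from the denominator.

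**The case against.** The case for leaving the rule alone has four parts.

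- **Other rules may catch the patient.** A dive stopped for panic or ear pain may well count as a subject request, an unacceptable adverse event or a physician's decision under 3.4.1, and the patient would then not be evaluable. This stands in part. A reader might infer that every aborted dive followed by prompt SRS is scored a success; the documents do not support that, since some such patients would be withdrawn. But withdrawal is not automatic, and replacement hides the HBO failure instead of counting it.
- **Incomplete dives may be rare.** The 15% in 4.2 is the estimated share who may be unable to equalize at the test dive, before a tympanostomy tube is offered. It is not a treatment-day failure rate and should not be read as one. Claustrophobia resistant to medication is an exclusion (3.2), and 4.3 anticipates no HBO toxicity. This stands. It is not a complete safeguard: 14.3 describes the familiarization dive as pressurized to 2.4 ATA and released, with no hold stated, so it does not test 30 minutes of confinement.
- **The timing may be easy.** The cited head-and-neck experience averaged about 8 minutes, although 6.1 expects SRS set-up to be more complex. If t is 0.80 or more, the effect is small. This stands, and the fall from 0.755 to 0.447 should not be quoted alone.
- **Coordination was the chosen question, and exposure may be recorded anyway.** The case report form is not supplied, and 8.2 lists data from automated instruments among source records. So it cannot be said that exposure will go unrecorded, only that the protocol does not ask for it or use it.

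A reader might also infer that poor HBO tolerance can never trigger the interim rules. That goes too far: a problem that delays or prevents SRS would count, and the first look in 7.4 refers to patients, not evaluable patients.

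**Conclusion.** The point holds in limited form. Nothing in 2.2, 6.1, 7.4 or 3.4.3 makes delivery of the planned exposure a condition of success or of being evaluable, although the stated rationale depends on it. The gap covers two groups: patients with a shortened dive who go on to timely SRS without withdrawal, and patients withdrawn for HBO intolerance and replaced.

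Its size depends on two unstated rates. With 10% of dives incomplete, the probability of declaring feasibility falls by 0.199 at t = 0.60 (0.755 − 0.556), 0.117 at t = 0.70 (0.952 − 0.835) and 0.027 at t = 0.80 (0.997 − 0.970). If incomplete dives are rare or timing is easy, the conclusion would seldom change; near the bar, one patient decides it. The calculation assumes independence. If shortened dives tend to delay SRS, the current rule already fails some of them and the gap is smaller.

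The documents do not show that the trial will reach a wrong conclusion. They show that its rule cannot separate delivered from undelivered HBO. The change is worth making because it is cheap and concerns the sole primary endpoint.

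**What to change.** - **2.2, 6.1 and 7.4:** define a feasibility success as the HBO session delivered as the protocol specifies and T1 of at most 30 minutes. The investigators should pre-specify what counts as delivered, working from 4.2 and 14.3; this review does not propose a criterion.
- **3.4.3:** state that a patient who starts the treatment-day HBO session stays in the feasibility denominator and is not replaced for that endpoint if the session is aborted. Without this, a withdrawn patient would still leave the count and the joint definition would be undercut. Replacement for the secondary comparison can stay as planned.
- **Treatment-visit data:** take achieved pressure and time at depth from the chamber record, and report delivery and timing separately as well as jointly.

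The cost is wording in four sections and two data fields. The reported success rate may be somewhat lower. No change to the HBO regimen is proposed.
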